1. Train DNNs to generate brain-like dynamics during naturalistic stimuli (i.e. movies and video games). The hypothesis is that large DNNs can be trained to accurately reproduce brain dynamics (auto-encoding), by learning connections in a space restricted by priors on anatomo-functional

- connectivity generated using individual experimental measures.
2. Train DNNs to jointly generate brain-like dynamics as well as perform supervised learning tasks in vision, language and memory domains. The hypothesis is that biological brain data will help train DNNs faster on the supervised task, using more limited number of training samples than in the absence of biological brain data.
 3. Transfer a DNN trained on a specific task to a task from a different domain, e.g. from vision to language. The first layers of the DNN will be identical for both task, but the highest layers will be trained in a task-specific fashion. The hypothesis is that, by using biological brain data in the training, the underlying architecture will be flexible even if initially trained in a specialized domain. Transfer learning will therefore work efficiently, achieving accurate and fast learning.

Theoretical background

Artificial deep neural networks. DNNs are mathematical models loosely inspired by biological networks. The type of DNNs that will be used in this project are trained using mathematical optimization tools to perform *supervised* tasks. This typically means that a large number of labeled data is available, e.g. the ImageNet¹ (Fei-Fei et al., 2010) database which features pictures organized by categories. The parameters of the DNNs are iteratively adjusted such that it is able to match data points, e.g. images, to labels, e.g. image categories. These artificial neural networks are called “deep” because they are structured with many layers of formal neural units, while originally only “shallow” architectures with a few layers had been successfully trained. The AlexNet² architecture was a turning point, demonstrating that a deep network featuring 8 layers could substantially improve the state-of-the-art on ImageNet (Krizhevsky et al., 2012). Both the number of layers and the performance have kept increasing since, with networks including tens of millions of parameters and up to 1000 layers attaining very low error rates on ImageNet (He et al., 2016).

[figure not shown]

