¹⁶ <https://github.com/poldracklab/fmrip>

al., 2014). A detailed description of the fmripipeline is available online¹⁷.

Standard MEG data cleaning (ICA-based ocular, cardiac and muscle artefact rejection, and exclusion of bad segments/channels) will be followed by data segmentation with respect to events of interest. A MEG-compatible eye-tracker, in combination with EOG traces, will be used to control for unwanted artefacts or synchronizations generated by eye movements (e.g. saccades). MEG data-preprocessing and analyses will be conducted using a combination of open-source tools developed in the [name] lab (NeuroPycon¹⁸, Visbrain¹⁹, Brainpipe²⁰, and TensorPac²¹, as well as well-established freely-available toolboxes, i.e. MNE-python (Gramfort et al., 2013).

Artificial neuronal models

Regarding aim 1, we will develop “vector-quantized variational auto-encoders” (VQ-VAE) that compress the brain images over a time window of 15 seconds, using discrete latent variables (van den Oord et al., 2017). The training of the VQ-VAE will be implemented using all the video and video game fMRI data available for each subject, and a separate model will be trained for each subject. Compressed representation of the video and audio signals, as well as text transcripts of the video will be generated using established techniques (Richard, H, Pinho, AL, Thirion, B, Charpiat, G, 2018). We will then train a sparse attentive backtracking (SAB) recurrent neural network on these discrete latent variable representation to predict future fMRI time series from past time points, using a mixture of past video, audio and functional signals. The performance of the recurrent DNN will be evaluated by the accuracy of prediction of future fMRI time points from past fMRI time points and compared to simple auto-regressive models as a benchmark, using split half cross-validation on available data (half of time points for training, half of time points to evaluate the accuracy of the model).

Regarding aim 2, the same VQ-VAE model trained for aim 1 will be trained to reduce the dimensionality of fMRI time series specifically on the data collected in the language, image, and memory tasks. A separate SAB recurrent DNN will be trained to solve the same task as required for humans. We will evaluate the ability to solve those tasks in isolation, using ten-fold cross validation to evaluate the performance of the models.

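### The protocol is inconsistent on which inputs the Aim 1 network has at evaluation, and its only benchmark has no stated stimulus term, so a win could not be attributed to the network

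*Protocol*

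**What the plan says.** The Aim 1 paragraph (Protocol, Artificial neuronal models) sets out a chain of steps for each subject. A VQ-VAE compresses the fMRI data over 15-second windows. Stimulus features are then prepared: "Compressed representation of the video and audio signals, as well as text transcripts of the video will be generated". A sparse attentive backtracking (SAB) recurrent network is trained on the compressed representation "to predict future fMRI time series from past time points, using a mixture of past video, audio and functional signals".

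The sentence after that turns to scoring. Performance is "evaluated by the accuracy of prediction of future fMRI time points from past fMRI time points" and "compared to simple auto-regressive models as a benchmark". Validation is split-half: "half of time points for training, half of time points to evaluate the accuracy of the model".

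The benchmark's inputs are not listed. The paragraph describes no benchmark with video or audio terms, no fMRI-only version of the network, no ablation and no forecast horizon.

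The hypothesis under test is the first specific aim in Summary and objectives. It says that large networks can reproduce brain dynamics during movies and video games, "by learning connections in a space restricted by priors on anatomo-functional" connectivity, with those priors derived from each individual's own measurements.

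**The concern.** A benchmark comparison isolates what a model adds only if both sides see the same information. As trained, the network sees the stimulus. An auto-regressive model, in the usual meaning of the term, sees only the past of its own series. Participants are watching videos or playing games, so some stimulus-driven signal is expected. Any model given lagged stimulus features, linear or not, could then beat AR without describing the dynamics any better.

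At stake is the interpretation of Aim 1. The finding that stimulus features help prediction could be reported as the finding that the network models brain dynamics. This also touches the fallback in Impact and outcomes, where the networks may still be useful as brain models if they explain enough variance in biological data. The Aim 1 prediction result is the closest evidence for that, and AR is its only benchmark.

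**Working it through.** **1. What there is to reproduce.** The protocol gives no accuracy figure, success threshold or effect size for the Aim 1 comparison. The check is therefore a reading of the text, followed by an illustration on assumed values.

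**2. The two sentences side by side.**

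| | Training sentence | Evaluation sentence |
|---|---|---|
| Network inputs | past video, audio, fMRI | past fMRI |
| Benchmark inputs | not applicable | not listed; AR implies past fMRI |

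Two readings are open.

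- *Video and audio are supplied at evaluation.* The network then has information that AR lacks, and the difference mixes input and architecture.
- *Only past fMRI is supplied at evaluation.* The inputs match, but the network scored is not being used as it was trained. The protocol does not say how the stimulus inputs are removed or whether a separate fMRI-only network is fitted.

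**3. Closed-form illustration of the first reading.** Let y(t) = φ·y(t−1) + u(t), predicted one step ahead, with u(t) white. AR leaves residual variance Var(u), and Var(y) = Var(u)/(1−φ²), so R²(AR) = φ². If past stimulus linearly explains a share s of Var(u), then R²(ARX) = 1 − (1−s)(1−φ²) = φ² + s(1−φ²). Both φ and s are assumptions.

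| φ | AR | ARX, s = 5% | s = 10% | s = 20% |
|---|---|---|---|---|
| 0.5 | 0.250 | 0.288 | 0.325 | 0.400 |
| 0.6 | 0.360 | 0.392 | 0.424 | 0.488 |
| 0.7 | 0.490 | 0.516 | 0.541 | 0.592 |

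For φ = 0.6 and s = 10%: 0.36 + 0.10 × 0.64 = 0.424.

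**4. Simulation with an autocorrelated stimulus.** The truth was y(t) = φ·y(t−1) + √share·s(t−1) + √(1−share)·noise, where s(t) is here the stimulus series, with unit variance. Each run had 20,000 time points and 5 lags, was fitted on the first half and scored on the second, and results were averaged over 5 seeds. AR used past y only; ARX used past y and past stimulus. Both are linear. Selected held-out R² values:

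| φ | Stimulus autocorrelation | Share | AR | ARX | Gain |
|---|---|---|---|---|---|
| 0.6 | 0.5 | 0% | 0.355 | 0.355 | 0.000 |
| 0.6 | 0 | 10% | 0.354 | 0.417 | 0.063 |
| 0.6 | 0.5 | 30% | 0.498 | 0.637 | 0.139 |
| 0.3 | 0 | 50% | 0.084 | 0.536 | 0.452 |
| 0.9 | 0.9 | 10% | 0.900 | 0.908 | 0.008 |

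The second row agrees with step 3 (0.063 against 0.064). With share zero the gain was zero throughout. For shares of 10% to 50% it ran from 0.008 to 0.452. In eight of the nine combinations of φ and stimulus autocorrelation the gain rose with the share. In the most autocorrelated one (0.9 and 0.9) it stayed at 0.008 to 0.009, because past y already carries most of the stimulus information.

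**5. The connectivity prior.** The hypothesis restricts the learned connections by anatomo-functional priors. The VQ-VAE and SAB descriptions under Artificial neuronal models mention no such restriction and no comparison with and without it.

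**The case against.** The strongest reply is that the benchmark is named in the same sentence that describes scoring from past fMRI. Read literally, both models are then compared on the same information. That stands: unequal inputs at evaluation are a possible reading, not an established fact. It does not settle the matter, because it conflicts with the training sentence and leaves unexplained how a network trained on video and audio is to be scored without them.

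Other points also stand:

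- The hypothesis does not claim that a recurrent network beats a linear model with equal inputs. Stimulus-driven response is part of brain dynamics during a movie, and AR is a legitimate floor. A win would be a real gain in prediction; only its attribution is open.
- The network works on compressed discrete codes, which could handicap it against AR, so the net bias in a real comparison is not known.
- The Sample size section defines the primary aim as training networks to solve a variety of tasks. The Aim 1 benchmark is not that test.
- Extra comparators can be run later on the same data and may appear in an analysis plan not shown here. The conflict over inputs is nevertheless in the protocol's own text.

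A reader might infer that the benchmark certainly receives less information, so that a win says nothing about brain dynamics. The evaluation sentence does not support that. A reader might also infer that transcripts feed the recurrent network. They are to be generated, but the training sentence lists only video, audio and functional signals.

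**Conclusion.** The point holds as an inconsistency that leaves the Aim 1 comparison open to two readings. If video and audio are supplied at evaluation, beating AR would show better prediction but not that the gain comes from the network. The size cannot be derived from the protocol. It is zero if the stimulus adds nothing beyond past fMRI and generally grows with the stimulus share. The illustrated gains of 0.008 to 0.452 rest wholly on assumed autocorrelations, shares and one-step linear dynamics. They show that the effect can occur, not how large it will be here.

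The connectivity-prior mismatch is a separate, secondary point: as described, the analysis does not test that part of the hypothesis. Severity: should-fix. Recruitment, scanning and sample size are unaffected.

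**What to change.** State which inputs the network receives at evaluation and make the training and evaluation sentences agree. Then match the benchmark to the inputs with two pre-stated comparisons, on the same split and at one stated forecast horizon:

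1. The full-input network against a regularised linear auto-regressive model with the same lagged video and audio features (ARX). If transcripts are in fact used, list them as inputs to both.
2. A network trained and scored on fMRI only, against plain AR.

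The first shows what the network adds once the stimulus is available to both sides. The second shows what it adds from past brain signal alone. The full-input network against plain AR can still be reported as a measure of total predictive gain, labelled as such.

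Separately, reconcile the Aim 1 hypothesis with the model description: either say where the connectivity restriction enters and compare fits with and without it, or remove it from the hypothesis.

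The two input-matched comparisons cost one extra linear model and one extra network fit per subject. Testing the prior, if it is kept, adds a further fit. All of this is computing time, with no new data and no added burden on participants. It should be fixed in writing before the Aim 1 results are seen.

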We will also include a video game task. It has been shown that skills acquired or trained through playing video games, can be transferred to various cognitive tasks relevant for everyday life. In a meta-analysis, Powers et al. (2013), found that video game play has an effect on auditory and visual processing skills, motor skills, and spatial imagery (refs). Similarly, Boot and colleagues (Boot et al. 2008) reported that action based video game players outperform non-video game players on visuospatial and working memory task, and similar results were found after action based video game training (Boot et al. 2008; Blacker et al. 2014, Green and Bavelier 2006, Green and Bavelier 2007). As such, playing video games can be considered a type of naturalistic stimuli, as it engages and strengthens various cognitive functions useful in day to day functioning. By contrast, DNNs have difficulties transferring skills acquired in one video game to another one, even when the new game shares very similar mechanics with the original game used for training (Nichol et al., 2018). By collecting extensive video game play in one participant, across various types of video games, we will be able to test if the DNNs trained on the data from one video game, have extracted features that can be used to achieve good performance on a variety of cognitive tasks, as well as on different types of video games (Aim 2). We will also be able to test if training on one of the videogame will increase the speed of learning on the other videogames, or cognitive tasks, and thus achieves superior generalization abilities compared to existing DNN architectures (Aim 3).

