The **image task** (13 minutes). Participants will be presented with images depicting real-world scenes, and judge whether they liked, disliked, or were neutral about the image. An MR-compatible mouse will record their choice. Images are selected from a large scale and diversity image datasets such as ImageNet¹¹, Common Objects in Context dataset¹², SUN database (Xiao et al., 2010), and the THINGS dataset. We selected images to cover a wide range of categories, based on ImageNet, with at least two different examples in each category. Images will be presented in event-related fMRI

The **memory task** (13 minutes), participants will be presented a randomized sequence of everyday images (selected from ImageNet), and control stimuli (an abstract multicolored image) for three seconds each. Images will appear in one of the four quadrants of the screen and participants will be asked to remember the images, as well as their position in the four quadrants (either top-left, top right, bottom-left or bottom-right). To control for attention, they will also be asked to press a key each time they see a stimuli. The encoding phase will last 13 minutes (Belleville et al., 2014). The retrieval will be done outside the scanner, and 10 minutes after the end of the encoding phase. Participants will be presented the same set of images from the scanner, in a new order, along with new images, all appearing in the center of the screen. They will have to determine whether each image has been previously presented, and if YES, where it was located (Belleville et al., 2014).

During **video game task** (30 to 60 minutes depending on the session type) participants will use an

¹⁰ <http://www.arringtonresearch.com/index.html>

¹¹ <http://www.image-net.org/>

¹² <http://cocodataset.org/#home>

MRI compatible video game controller built by [name], the UNF engineer. The video game controller uses fiber optics to minimize the likelihood of artifacts in the MRI scanner, and the shell of the controller is 3D printed using an in-house printer. While being scanned participants will be to play video games, such as Shinobi III¹³. The games, as well marker of the participants' style of play (i.e. button presses, number of jumps, runs, lunges, ducks, etc), and game stats will be recorded and saved for later analysis.

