Regarding aim 3, we will use the VQ-VAE model trained on all of the movie data, and only train the SAB component of the recurrent DNN to solve each particular task. We will evaluate the performance of this variant of the model using ten-fold cross-validation (within each task) and expect this variant of the recurrent DNN to be easier to train and outperform the DNNs trained specifically on each task, as described in aim 2. This analysis will test directly that the representation learned on movies, or video games transfer well to other cognitive context (language, memory, image).

Sample size

The primary aim of this project is to demonstrate our ability to efficiently train artificial DNNs to solve a variety of task. Potentially this could be achieved with data collected on a single human participant. The limiting factor is here the amount of data available on each individual. The amount of individual data will exceed what was collected in the only comparable study we are aware of (Fong et al., 2018). We do not think we can realistically collect more data than currently planned, because of the large time demands already required from the research participants. To check that our observation generalize we would like to have three participants for each task, which we increased to four to anticipate participants potentially dropping out of the study. Because we will be testing three tasks in parallel, the core cohort will therefore include 12 subjects.

¹⁷ <https://fmripipeline.readthedocs.io/en/stable/citing.html>

¹⁸ https://neuropicon.github.io/neuropicon_doc/

¹⁹ <http://visbrain.org/>

²⁰ <https://etiennecmb.github.io/brainpipe/>

²¹ <https://etiennecmb.github.io/tensorpac/>

References

- Boot, W.,R., Kramer, A., F., Simons, D., J., Fabiani, M., & Gratton G., 2008. The effects of video game playing on attention, memory, and executive control. *Acta Psychologica*, 129, 387–398.

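### The Aim 2 analysis has no network trained without brain data and only one training size, so as written it does not test the Aim 2 hypothesis

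*Protocol*

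**What the plan says.** The hypothesis is in the protocol's Summary and objectives, specific aim 2. Brain data are expected to speed up training on the supervised task and to do so "using more limited number of training samples than in the absence of biological brain data".

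The analysis is in Artificial neuronal models, in the paragraph on aim 2, and has three steps:

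- First comes compression of the brain signal. The VQ-VAE is carried over from the first aim and "will be trained to reduce the dimensionality of fMRI time series specifically on the data collected in the language, image, and memory tasks".
- Next comes the network that performs the task, described in one sentence: "A separate SAB recurrent DNN will be trained to solve the same task as required for humans".
- Last comes the assessment, again in one sentence and with no comparator mentioned: "We will evaluate the ability to solve those tasks in isolation, using ten-fold cross validation to evaluate the performance of the models".

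Comparators appear in three other places:

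- **Aim 1, same section.** The recurrent network's prediction of future fMRI is "compared to simple auto-regressive models as a benchmark, using split half cross-validation on available data".
- **Aim 3, same section.** The VQ-VAE is trained on the movie data and only the SAB part is trained on each task. The investigators "expect this variant of the recurrent DNN to be easier to train and outperform the DNNs trained specifically on each task, as described in aim", the aim meant being the second.
- **Theoretical background, the video game paragraph.** It hopes for a network that "achieves superior generalization abilities compared to existing DNN architectures (Aim 3").

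**The concern.** The Aim 2 hypothesis makes two comparative claims: learning with brain data is faster than learning without it, and it needs fewer samples. Testing them takes a network trained without brain data, and a measure of samples or training effort. The Aim 2 paragraph supplies neither. It yields a held-out performance figure per task, with nothing to set it against.

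Such a figure is equally compatible with brain data helping, hurting or making no difference. This matters because the Sample size section gives efficient training of networks as the project's primary aim, and Aim 2 is where the benefit of brain data over no brain data is claimed.

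**Working it through.** No power calculation is involved. The only sample-size figure is the core cohort. The Sample size section gives four participants per task (three, plus one for dropout) and three tasks: 4 × 3 = 12, which matches the stated 12. The point below does not depend on it.

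**Step 1. What the hypothesis needs against what is planned**

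| Needed for Aim 2 | Planned in the Aim 2 paragraph |
|---|---|
| Matched network without brain data | None named |
| Several training-set sizes, or samples to a criterion | None; ten-fold cross-validation only |
| Measure of training speed | None |

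**Step 2. Whether another comparator fills the gap**

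- The Aim 1 benchmark is an auto-regressive model of fMRI time series. Its outcome is prediction of fMRI, not performance on the language, image or memory task.
- The Aim 3 contrast sets a VQ-VAE trained on movie data against the task-trained networks of Aim 2. The VQ-VAE compresses brain images in both, so both sides use brain data.
- The comparison with existing architectures is mentioned for video games and assigned to Aim 3. The analysis section does not take it up.

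The number of planned comparators without brain data for Aim 2 is therefore 0.

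**Step 3. What ten-fold cross-validation can show**

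With k = 10 folds, each fold trains on (k − 1)/k = 9/10 = 90% of the data. The fraction is the same in all ten folds, so there is one distinct training size and one point on the learning curve.

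**Step 4. Why one point is not enough (illustration with assumed figures)**

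Assume N = 1000 labelled samples, so 900 per training fold, and error that falls as a power law, error(n) = a·n^(−b). Assume also a cross-validated error of 0.20 at n = 900. Then a = 0.20 × 900^b, and the number of samples needed to reach an error of 0.30 is

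n = 900 × (0.20/0.30)^(1/b).

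| Assumed exponent b | Error at n = 900 | Samples to reach error 0.30 |
|---|---|---|
| 0.3 | 0.20 | 900 × (2/3)^(1/0.3) ≈ 233 |
| 0.5 | 0.20 | 900 × (2/3)^2 = 400 |
| 0.8 | 0.20 | 900 × (2/3)^(1/0.8) ≈ 542 |

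The three curves give the same cross-validated result, yet the samples needed differ by a factor of 542/233 ≈ 2.3. Adding a comparator without brain data at the single 90% size would still leave the claim about fewer samples unanswered. Both elements are needed.

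**The case against.** **The wording is loose.** The SAB network is called separate, it is not explicitly said to receive fMRI, and performance is assessed in isolation. One could read this as a control without brain data. The more natural reading is separate from the Aim 1 network and one task at a time. The Aim 3 paragraph supports it by treating the SAB as a component of the same recurrent network. On either reading no contrast with a network lacking brain data is stated.

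**The detail may sit in a statistical analysis plan.** A grid of training sizes could. But the protocol fixes its own Aim 2 analysis (models, evaluation, validation scheme), and that analysis does not match its own hypothesis. Aims 1 and 3 each name a comparator; Aim 2 does not. The missing comparator is the firmer half of the point.

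A reader might also infer more than the protocol supports:

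- *That the hypothesis is untestable.* A network without brain data needs only the stimuli and labels, so the limit lies in the written analysis and not in the data.
- *That efficiency is measured nowhere.* The project overview and the Aim 3 paragraph mention speed of learning and ease of training. They give no measure and belong to Aim 3, so they do not rescue Aim 2, but the idea is not absent.
- *That the network would simply decode the participant's button press.* The protocol does not say whether fMRI is an input at test, and specific aim 2 describes networks that generate brain-like activity. In the memory task, retrieval takes place outside the scanner, and the key press during encoding carries no answer. Decoding of responses is possible only in the language and image tasks, and only if fMRI is fed in at test.
- *That accuracy on the image task is meaningless.* Participants "judge whether they liked, disliked, or were neutral about the image", which has no objectively right answer. A participant's own rating is still a usable label, and the language task is likewise a judgement of similarity. Substituting database categories would redesign the task and depart from having the network do what the participant did.

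**Conclusion.** The point holds for the analysis as written. Specific aim 2 is a with-versus-without claim about speed and samples, while its planned analysis has no arm without brain data, one training size (90% of the data), and no measure of training speed. No other comparator in the protocol supplies what is missing. Followed as written, the plan cannot support a conclusion on Aim 2 in either direction.

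This rests on reading the Aim 2 paragraph as a complete statement of that analysis. The 233, 400 and 542 samples are illustrative and depend on an assumed sample number, error level and curve shape. The finding that there is one training size does not depend on them. The gap should be closed before the Aim 2 analysis is run. It can be closed without loss after data collection, because it affects only how networks are trained and compared.

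**What to change.** In the Aim 2 paragraph of Artificial neuronal models:

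1. Name the comparator: the same architecture, trained on the same stimuli, labels and folds, without brain data.
2. Train both networks at several training-set sizes, keeping the held-out folds the same.
3. Make the Aim 2 measure the within-subject difference in samples (or iterations) needed to reach a held-out accuracy fixed in advance.
4. State whether fMRI is an input at test. If it is, responses made in the scanner during the language and image tasks could be decoded from the signal, so evaluate the contrast with stimuli only, with brain data entering during training.

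A further arm trained on time-shifted brain data would separate the effect of matched brain activity from that of extra data volume. It is a useful option but is not needed to resolve the mismatch.

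The cost is extra computing and a short change of wording, with no new scanning or participants. The headline result becomes a difference, which may turn out to be null.
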